2.2 Secondary Objectives

1. To determine whether RBUS with UJA, in conjunction with standard of care history, physical examination and laboratory studies confers the same diagnostic information as the gold standard, non-contrast CT.
2. To determine the natural history and rate and time of stone passage for ureteral stones of differing locations (proximal, mid or distal ureter) and sizes (<2mm, 2-4mm, 5mm, 6-7mm, 9-10mm).

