thin renal parenchyma. In addition, the presence or absence of hydroureter (proximal ureter, above the iliac bifurcation and distal ureter, below the iliac bifurcation) will be documented. If there is a stone in the renal pelvis, it will be recorded as interpolar kidney and noted as renal pelvis. For any case, if the reader believes that a particular stone is the cause of the participant's symptoms, then this will be noted. This is particularly useful in cases in which there are multiple stones. The bladder will be examined in the transverse plane at the level of the trigone to view both jets simultaneously. All participants will be scanned for 5 minutes. The number of jets from each ureteral orifice will be tabulated over time so that ureteral jet frequency, defined as number of jets per minute, can be calculated. Patients will be categorized into three groups. Group I- no ureteral jets on the symptomatic side; Group II- continuous low-level ureteral jet on the symptomatic side; Group III- ureteral jets similar to nonsymptomatic side.

In order to determine if RBUS with UJA along with clinical data confers non-inferior information compared to non-contrast CT, objective findings such as laboratory data including BMP, CBC, urine analysis and physical exam obtained as part of routine care will be retrieved from the patient's medical record and reviewed retrospectively. Clinical data and RBUS results will be de-identified/coded and the Urologist will be blinded to the CT results. Diagnosis and treatment recommendations will be determined based upon these findings and compared to those attained by CT to assess for congruence. Statistical analysis will be performed to determine non-inferiority between the studies.

Stone size and location based on CT will be recorded at the time of enrollment into the study and time to stone passage will be recorded. All study participants will be followed for stone passage. Time to stone passage will be stratified according to stone location (proximal, mid or distal ureter) and size (<2mm, 2-4mm, 5mm, 6-7mm, 9-10mm).

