7.2 Study Design

This is a single institution, prospective study to evaluate the prognostic significance of RBUS with UJA, and its utility in providing non-inferior information compared to non-contrasted CT, as well as to evaluate the spontaneous stone passage rate of ureteral stones. The study will be conducted at Washington University and will enroll approximately 100 participants over two years.

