7.3 Data Analysis

Primary objective:

This patient cohort will be analyzed retrospectively to determine whether US with UJA is predictive of spontaneous stone passage versus need for surgical intervention. Kaplan-Meier curve will be used to test time to spontaneous stone passage between the two groups. A chi-square test of independence will be used to test intervention rates between the two groups. A multivariate analysis will also be conducted controlling for such variables as age, gender, BMI, side, size of stone, and stone passage. A Cox-proportional hazards model will be used for time to spontaneous stone passage and logistic regression will be used for intervention.

Due to the unforeseen difficulty of recruitment and the uncertain assumptions of the initial power analysis, an interim statistical analysis is recommended to be performed when the recruitment reaches 50 patients. Based on the results, a decision will be made whether to continue recruitment to the initial 100 targeted patients, adjust the number of targeted patients based on a new power analysis, or to discontinue recruitment. The interim results

should not affect primary independent variables in the study as the radiologist performing the ultrasounds will not have access to the results.

Secondary objective 1:

Statistical analysis will be performed to determine diagnostic and treatment concordance between the two methods. A multivariate logistic regression model will also test patient factors that are associated with discordant results.

Secondary objective 2:

In a prospective manner, they will be followed to determine the natural history of ureteral stones with regard to stone passage. Average time to stone passage for each size category and stone location will be determined. Cox-proportional hazard models will be used to determine significant factors affecting time to stone passage.

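### Secondary objective 1 claims non-inferiority to CT, but Section 7.3 plans only undirected concordance and pooled discordance, so missed interventions are not separated from over-calls

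*Combined protocol and SAP*

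**What the plan says.** The objective is worded in more than one way. Section 2.2 asks whether ultrasound with jet assessment, together with history, examination and laboratory data, "confers the same diagnostic information as the gold standard, non-contrast CT". Sections 7.1 and 7.2 ask for non-inferior information compared with CT, and Section 5.2 states: "Statistical analysis will be performed to determine non-inferiority between the studies".

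The comparison is described in Section 5.2. A urologist blinded to CT works from the clinical data and the ultrasound: "Diagnosis and treatment recommendations will be determined based upon these findings and compared to those attained by CT to assess for congruence". Section 7.1 mentions the CT diagnosis as the comparator and does not say how a CT-based treatment recommendation is produced.

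The analysis is in Section 7.3: "Statistical analysis will be performed to determine diagnostic and treatment concordance between the two methods". One further sentence follows: "A multivariate logistic regression model will also test patient factors that are associated with discordant results". No section names a concordance statistic or a margin, provides for sensitivity, specificity or a miss rate, or splits discordance by direction.

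**The concern.** Non-inferiority asks whether ultrasound is worse than CT. Concordance asks only whether the two agree. For a treatment recommendation there are two ways to disagree. In a miss, CT leads to intervention and ultrasound does not; in an over-call, the reverse holds. Percent agreement adds the two together. The logistic model on discordant results does the same, because it codes both as one event. A factor that raises misses and lowers over-calls could then show little or no association.

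The treatment recommendation is where this matters. Section 3.1 requires a CT-diagnosed ureteral stone, so disagreement on whether a stone is present can go only one way. Disagreement on treatment can go both ways.

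Sections 1.2 and 5.4 present ultrasound with jet assessment as a possible alternative to radiation-based imaging. For that use, a reader needs to know how often patients whom CT would send to intervention are not identified. The planned analysis does not commit to reporting that figure.

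**Working it through.** **Inputs.** N = 100, from Section 7.2 ("will enroll approximately 100 participants over two years"). A smaller final number is possible, since Section 7.3 says "an interim statistical analysis is recommended to be performed when the recruitment reaches 50 patients" and allows recruitment to stop there. The share p of patients CT would treat is not given, so it is assumed and varied from 10% to 50%. There is no planned figure to reproduce for this objective: no margin, error rate or power is stated.

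**Formulas.** With sens = the proportion of CT-intervene patients for whom ultrasound also says intervene, and spec = the proportion of CT-not-intervene patients for whom ultrasound also says not:

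- agreement = p × sens + (1 − p) × spec
- miss rate = 1 − sens; over-call rate = 1 − spec
- kappa = (agreement − expected) / (1 − expected)

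**Step 1: same agreement, opposite errors.** N = 100, p = 20% (20 CT-intervene, 80 not).

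| Scenario | Agreement | Expected agreement | Kappa | Miss rate (exact 95% CI) | Over-call rate (exact 95% CI) |
|---|---|---|---|---|---|
| 10 misses, 0 over-calls | 90/100 | 0.2×0.1 + 0.8×0.9 = 0.74 | 0.16/0.26 = 0.62 | 10/20 = 50% (27-73%) | 0/80 = 0% (0-5%) |
| 0 misses, 10 over-calls | 90/100 | 0.2×0.3 + 0.8×0.7 = 0.62 | 0.28/0.38 = 0.74 | 0/20 = 0% (0-17%) | 10/80 = 12.5% (6-22%) |

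Percent agreement is the same in both rows. This does not depend on p: ten disagreements out of 100 give 90% whichever way they fall. Kappa differs somewhat but does not show the direction, and a kappa of 0.62 accompanies a 50% miss rate.

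**Step 2: how far agreement can hide misses.** Half of the CT-intervene patients are missed (sens = 0.5).

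| Assumed p | Agreement, no over-calls | Kappa, no over-calls | Agreement, 5% over-calls |
|---|---|---|---|
| 10% | 95% | 0.64 | 90.5% |
| 20% | 90% | 0.62 | 86% |
| 30% | 85% | 0.58 | 81.5% |
| 40% | 80% | 0.55 | 77% |
| 50% | 75% | 0.50 | 72.5% |

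With no over-calls, agreement is 1 − 0.5p, so 90% or more needs p ≤ 20%. With 5% over-calls it is 0.95 − 0.45p, so 90% or more needs p ≤ 0.05/0.45, about 11%.

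**Step 3: precision of the miss rate.** With half missed at N = 100, the exact 95% intervals are 19-81% (5/10, p = 10%), 27-73% (10/20, p = 20%) and 31-69% (15/30, p = 30%). At N = 50 and p = 20% the interval is again 19-81% (5/10).

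**Step 4: what a margin would require.** As an illustration only, suppose the aim is to show a miss rate below 20% when the true rate is 5% (exact binomial test, one-sided 0.025, 80% power). This needs 41 CT-intervene patients: with at most 3 misses allowed, the error rate is 0.024 and the power 0.85. Dividing 41 by p and rounding up, the total is 410, 205, 137 or 82 at p = 10%, 20%, 30% or 50%. One hundred participants suffice only if p is about 41% or more.

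**The case against.** The strongest reply is that the text is open rather than wrong. Section 7.3 covers diagnosis as well as treatment and does not name percent agreement. Concordance could be reported as kappa or a full 2x2 table, and Section 5.2 separately promises a non-inferiority analysis. Section 2.2 asks for the same diagnostic information, for which agreement is a natural measure. All of this is true, but it does not settle the point. Nothing commits the analysis to a directional measure, kappa is not directional either, and the one model that is named pools the two kinds of error.

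A reader might infer that the objective will be judged on overall treatment agreement dominated by patients under observation, so that high agreement will hide a poor miss rate. The documents do not support that. They give no share of patients whom CT would treat. The one related figure, 95% passage in Section 1.1, concerns stones under 4 mm, while stones up to 10 mm are eligible. At a share of 40-50%, missing half gives 75-80% agreement or less, which is not obviously high.

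Two practical objections also stand. A multivariable model on about 10 misses would not be workable. McNemar's test compares the numbers of misses and over-calls, so it can be null when both are large.

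**Conclusion.** The concern holds in a conditional form. The mismatch between a directional claim and an undirected, pooled analysis is in the text and needs no assumption. Nor does the arithmetic that equal numbers of misses and over-calls give equal percent agreement.

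The size of the masking does rest on an assumption. With half of the CT-intervene patients missed and no over-calls, agreement is 90-95% if CT would treat 10-20% of patients, and 75-80% if it would treat 40-50%. Over-calls lower these figures further.

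The absence of a margin is part of the same problem: no result, directional or not, can support non-inferiority without one. This is a secondary objective and the change is small, so it should be made but does not threaten the trial as a whole.

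**What to change.** In Section 7.3, secondary objective 1:

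- State how the CT-based treatment recommendation is obtained, and classify both recommendations as intervene or not intervene.
- Cross-tabulate the two in a paired 2x2 table. Report the miss rate (ultrasound not intervene among CT intervene) and the over-call rate (ultrasound intervene among CT not intervene) separately, each with an exact 95% interval. Keep overall agreement and kappa as description.
- Tie any non-inferiority wording in Sections 5.2, 7.1 and 7.2 to the miss rate against a margin fixed before analysis. If no margin can be justified, report estimates and intervals only and drop the non-inferiority wording.
- Describe factors associated with misses and with over-calls separately, and fit a multivariable model only if there are enough events. McNemar's test is optional, since it tests imbalance and not the miss rate.

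The cost is mainly wording, because Section 5.2 already plans to compare the recommendations. If no CT-based treatment recommendation is recorded, a further reading of the CT cases may be needed. The statistical price is a small denominator for the miss rate: about 10-30 patients at N = 100 if the share is 10-30%, and half that if recruitment stops at 50. The interval will be wide, and the headline figure may look less favourable than overall agreement.

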The prognosis of a ureteral stone as can be conveyed to the patient is based on a historical study from Miller and Kane. In 1999, the authors studied 75 patients with ureteral stones ranging from less than 2mm to 10mm over approximately 6 weeks' time. It was found that smaller, more distal stones pass sooner and that stones <4mm pass 95% of the time, although this may take up to 40 days [13]. Since that time, multiple studies have shown medical expulsive therapy (MET) to be effective for earlier stone passage [14, 15, 16]. No modern investigation of stone passage rates based on size has been performed in the MET era.

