7.0 STATISTICAL CONSIDERATIONS

7.1 Study Objectives and Endpoints

Primary Outcome:

To determine if RBUS with UJA is prognostic of stone passage versus need for

surgical intervention:

1. Passage of stone as assessed by patient self-report and/or collection of stone or imaging.
2. Need for further medical attention as collected by chart review and phone interview for ED visit, hospitalization, or need for surgical intervention during the 42-day follow-up period.

Secondary Outcomes:

1. To determine if RBUS with UJA, in conjunction with standard of care laboratory data and history and physical confers non-inferior information compared to non-contrasted CT:
 - a. Urologist will review the patient's de-identified/coded history and physical, laboratory studies, and RBUS with UJA and make an assessment and treatment recommendations. The urologist will be blinded to the results of the CT. Comparison will be made between the CT diagnosis and the blinded assessment of the urologist.
2. To determine if the natural history and rate and time of stone passage for ureteral stones of differing locations (proximal, mid or distal ureter) and sizes (<2mm, 2-4mm, 5mm, 6-7mm, 9-10mm):
 - a. Assessment of the stone location and size to be conducted by a radiologist.

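### Passage rates by stone size and location are promised, but only an undefined average time is planned for each stratum, and 8 mm stones have no size class

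*Combined protocol and SAP*

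**What the plan says.** Section 2.2 sets as its second secondary objective the "rate and time of stone passage for ureteral stones of differing locations" and sizes. Section 7.1 repeats it ("To determine if the natural history and rate and time of stone passage for ureteral stones of differing locations"), and section 7.2 lists among the design aims "as well as to evaluate the spontaneous stone passage rate of ureteral stones".

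For this objective section 7.3 names two analyses: "Average time to stone passage for each size category and stone location will be determined" and "Cox-proportional hazard models will be used to determine significant factors affecting time to stone passage". Section 5.2 says that time to passage will be stratified by location and size but names no estimator. The only Kaplan-Meier analysis belongs to the primary objective and compares groups that are not size or location strata: "Kaplan-Meier curve will be used to test time to spontaneous stone passage between the two groups".

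Sections 2.2, 5.2 and 7.1 give the same five size classes: under 2, 2–4, 5, 6–7 and 9–10 mm. Section 3.1 admits any stone burden up to and including 10 mm.

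**The concern.** The rate is what the protocol says the field lacks. The benchmark in section 1.1 is a rate by size, "stones <4mm pass 95% of the time, although this may take up to 40 days", presented as the basis for what a patient can be told. The same section adds: "No modern investigation of stone passage rates based on size has been performed in the MET era". An average time cannot update a rate.

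The average is also undefined. Section 7.3 does not say whether it is a mean or a median, or how it treats patients who have surgery, still have the stone at day 42, or are lost to follow-up. If it is computed only from those who pass, it leaves out the patients who separate a stratum with a good prognosis from one with a poor prognosis. The study could then print similar times for strata with very different chances of passage.

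The missing 8 mm class means that some eligible patients would have no row in the by-size tables.

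**Working it through.** There is no figure in the plan to reproduce here. The check has three steps.

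**1. Promise against analysis.**
- Rate by size and location: promised in 2.2 and 7.1, with the passage rate also a design aim in 7.2. Section 7.3 names no proportion, denominator, cumulative incidence or interval.
- Time by size and location: promised in 2.2 and 7.1. Section 7.3 gives an average without a definition.
- Factors affecting time: covered by the Cox models. These can keep non-passers as censored, but they yield hazard ratios, and no per-stratum rate is planned from them.

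**2. What a passers-only mean can hide.** The 42-day horizon is from section 5.2, and the 95% passage figure is from section 1.1. All other passage and surgery percentages, and constant hazards, are assumptions. For 42-day passage P, surgery S and T = 42:
- total hazard L = −ln(1 − P − S)/T
- mean time among passers = 1/L − T·e^(−LT)/(1 − e^(−LT))
- restricted mean to day 42, with everyone not passed (surgery included) counted as 42 days = T − [P/(P+S)]·[T − (1 − e^(−LT))/L]

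Worked case, 80% passage and 5% surgery: L = −ln(0.15)/42 = 0.04517, so the passers' mean is 22.14 − 42 × 0.15/0.85 = 14.73 days. The restricted mean is 42 − (0.80/0.85) × (42 − 0.85 × 22.14) = 20.18 days.

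| Passage / surgery | Mean among passers (days) | Restricted mean (days) |
|---|---|---|
| 95% / 0% | 11.81 | 13.32 |
| 80% / 5% | 14.73 | 20.18 |
| 30% / 0% | 19.75 | 35.33 |
| 30% / 25% | 18.23 | 34.87 |
| 30% / 40% | 16.88 | 34.47 |
| 30% / 55% | 14.73 | 33.82 |

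Against the 95% stratum, the four 30% strata differ by 7.9 down to 2.9 days in the passers' mean, but by 22.0 down to 20.5 days in the restricted mean. Against the 80%/5% stratum, the passers' gap runs from 5.0 days to zero, and the restricted-mean gap from 15.1 to 13.6 days. The zero arises because, under constant hazards, the passers' mean depends only on P + S, which is 85% in both strata.

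**3. Size classes.** Whole millimetres map as follows: 1 to under 2; 2, 3 and 4 to 2–4; 5 to 5; 6 and 7 to 6–7; 9 and 10 to 9–10. Only 8 mm has no class. The same list stands in three sections, so a reading error in the text is unlikely.

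**The case against.** The strongest reply is that little is lost. The data are collected, passed-over-total can be computed at any time, and the objective is descriptive and secondary. That is true, but the plan commits to no rate, no denominator and no rule for surgery, so the reported figure would be chosen after the data are seen.

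A second reply is that the average need not be passers-only. Section 5.2 follows all participants for passage, and section 7.3 elsewhere uses methods that can keep non-passers. This stands: a survival-based average also fits the words, and the table's passers' column applies only to one reading. The exact tie at 14.73 days was also constructed. In the other cases shown, the passers' mean keeps the right direction but shrinks the difference. Even a survival-based average, however, is not a rate.

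A reader might go further in three ways that the documents do not support:
- That 8 mm patients are lost from all analyses of size. Section 7.3 adjusts its multivariate analysis for stone size and plans Cox models, and neither is tied to the five classes. For the same reason the hypothesis in section 1.2 about larger stones can still be tested.
- That many more stones, those measured in fractions of a millimetre, also lack a class. This depends on how CT size is recorded, which the documents do not state; a class labelled simply 5 mm suggests whole millimetres.
- That the primary Kaplan-Meier curve is wrong. Section 7.3 does not say how surgery enters it, but that is an unstated convention and not a demonstrated error. Surgery is analysed separately there by chi-square and logistic regression.

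**Conclusion.** The point holds as an analysis gap in a secondary objective. Section 7.3, followed as written, does not produce the promised passage rate by size and location, and its one per-stratum summary is undefined. Eligible 8 mm stones have no class in the categorical summaries. Both statements rest on the text alone.

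How misleading the average would be cannot be known from the documents. It depends on the reading taken, on unstated surgery rates and on the constant-hazard assumption. Nor is the net direction of error fixed: section 5.2 substitutes an imaging date when the passage date is unknown, which can lengthen recorded times. The primary comparison is unaffected.

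**What to change.** In section 7.3, secondary objective 2:

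- For each size class and each location, report the 42-day cumulative incidence of spontaneous passage over all enrolled patients in the stratum, with a 95% CI. Count surgery before passage as not passed (a competing event), and censor patients lost to follow-up at last contact. With no losses this is simply passers over the stratum total.
- Replace the average with the median time to passage where reached, or with the restricted mean to day 42, patients not passed (surgery included) counting as 42 days. The convention must be written down: in the 30%/55% case it gives 33.8 days, against 30.6 if surgery is censored.
- If a mean among passers is kept, label it as such and print passers out of the stratum total.
- Make the size classes exhaustive up to 10 mm, identically in 2.2, 5.2 and 7.1, for example by placing 8 mm in an adjacent class (such as 8–10 mm) and stating that CT size is rounded to whole millimetres. The documents do not show which class was intended, so that choice is the sponsor's.

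The cost is wording and a little analysis work, since time to surgery and CT size are already recorded. Cumulative incidence will reflect local surgical practice, and the report should say so. Imaging-dated passages remain a limitation. The intervals will be wide: with about 100 patients spread evenly over five classes (an assumption, 20 each), exact 95% limits are 56–94% for 16/20 and 12–54% for 6/20. If recruitment stopped at the 50-patient interim (10 each), 8/10 would give 44–97%.

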1.2 Rationale

Due to the increasing use of CT and concern for radiation exposure, it is important to consider alternative diagnostic imaging modalities. We seek to evaluate patients who present to the Barnes-Jewish Hospital (BJH) ED and to the Urology office with renal colic who have been diagnosed with a ureteral stone. We seek to determine whether the findings on ureteral jet assessment (UJA) by RBUS are predictive of a patient's clinical outcome. Specifically, we seek to

evaluate whether the presence, absence or relative strength of the ipsilateral ureteral jet can predict spontaneous passage versus need for surgical intervention over a 42-day (6-week) time period. As many patients have a life-long affliction with nephrolithiasis[1], the potential for a considerable aggregate accumulation of radiation exposure over their lifespan can be excessive and should not be overlooked [5, 7, 8]. This patient population, especially those first diagnosed at a young age, would benefit from imaging modalities that do not involve radiation.

Evaluating the significance of UJA and RBUS in patients with renal colic will help define the role of this imaging modality, as an alternative to ionizing radiation-based studies. The prognosis of urolithiasis based on UJA will be defined, as well as the natural history of stones managed expectantly. We hypothesize that UJA showing weak or absent ureteral jet will predict obstruction and a higher rate of surgical treatment compared to spontaneous passage. We hypothesize that larger stones will be less likely to pass without surgical intervention.

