3.0 PATIENT SELECTION

3.1 Inclusion Criteria

Patients must meet all of the following inclusion criteria to be eligible for study participation:

1. Age 18 and older at the time of consent
2. Willing and able to sign consent
3. CT diagnosis of ureteral stone with a stone burden less than or equal to 10mm

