5.0 STUDY PLAN

5.1 Screening and Informed Consent

Subjects will be seen and counseled by either the attending ED physician or their Urologist as part of the normal course of practice. Patients may be approached about study participation as soon as ureteral stone is suspected based on clinical presentation. Following CT diagnosis of ureteral stone, study team will further discuss study participation with the patient and complete the consent process if the patient is willing to participate.

The discussion regarding study participation will take place in a private setting, such as in a private consult room, to maintain confidentiality. HRPO approved consent form will be used to guide the consent process and document participant's consent. During the consent

process, the study team will explain RBUS with UJA, the normal anticipated course of a patient with the represented stone burden, potential risks and benefits of study participation, compensation and study follow-up schedule. Patients will be encouraged to ask questions and discuss the study with family. They will be given ample time to review the consent. It is possible that some participants may be contacted by phone to assess their interest in this study. If the participant expresses interest in the study, informed consent form will be mailed/e-mailed to him/her. This will be done in an effort to allow the patient ample time to read the consent at home, consider the study and discuss it with friends and family. This will not replace the face-to-face consent discussion the research team will have with the patient prior to signing the consent form.

Patients may decline to participate without an impact on their care. They will not be pressured to participate. No study related procedures will take place prior to the completion of the informed consent process and participant signing the HRPO approved consent.

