5.2 Study Plan and Procedures

Study RBUS with UJA will be obtained within 10 days following CT diagnosis of ureteral calculus. Ureteral jet data will be documented and patients will be followed prospectively for 42 days at 2 weeks, 4 weeks and 42 days (6 weeks) after diagnostic CT. Specifically, patients will be followed for spontaneous stone passage and will be expected to record date of stone retrieval. If specific date of stone passage is not known, date of standard of care imaging confirming absence of stone(s) will be used as the date of stone passage. If spontaneous stone passage is not achieved, patients will be counseled regarding further standard of care treatment options including surgical stone removal. If surgical intervention is indicated, time to surgical procedure will also be recorded. This patient cohort will be analyzed retrospectively to determine whether RBUS with UJA is predictive of spontaneous stone passage versus need for surgical intervention over a 42-day period.

Interpretation of RBUS and UJA:

Abdominal radiologists will interpret the RBUS research reads. All grey scale and color Doppler examinations will be performed by means of a commercially available unit with a 1-5 MHz phased array transducer or a 1-6 curved transducer. Flow toward the transducer is assigned a red color on Doppler. For grey scale evaluation, the presence or absence of urinary tract stones, size (longest axis in mm) and location- R, L, upper pole, interpolar and lower pole of the kidneys, proximal ureter, distal ureter and bladder- will be documented. The level of the renal pelvis represents the interpolar kidney with upper and lower pole above and below this level. For this study, a urinary tract stone will be termed an echogenic focus that demonstrates either posterior acoustic shadowing and or twinkle artifact on color Doppler images. In addition, presence of hydronephrosis (mild, moderate, and severe) will be documented. For the purpose of this read, hydronephrosis will be defined as such: mild hydronephrosis - urine fills the intra and extra renal pelvis and the major calyces are dilated; moderate hydronephrosis – above + dilatation of the minor calyx with preservation of the renal parenchyma; severe hydronephrosis – above +

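### Passage is timed from the diagnostic CT but patients can enter days later, so without delayed entry the stone-passage estimates of secondary objective 2 will run slow to the extent that pre-entry passers are lost

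*Combined protocol and SAP*

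**What the plan says.** Sections 5.2, 5.3 and 5.5 count follow-up from the diagnostic CT, with contacts at 2 weeks, 4 weeks and 42 days. Section 7.3 does not itself define time zero for time to passage, but the schedule strongly implies the CT.

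Entry comes later than the CT. Section 5.1: "Following CT diagnosis of ureteral stone, study team will further discuss study participation with the patient". Also in 5.1: "It is possible that some participants may be contacted by phone to assess their interest in this study". Those patients still need a face-to-face discussion before signing, and "No study related procedures will take place prior to the completion of the informed consent process". Section 5.2 then sets the outer limit for the scan: "Study RBUS with UJA will be obtained within 10 days following CT diagnosis of ureteral calculus". Section 5.3 starts the prospective telephone follow-up after the scan.

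On stone status, section 3.1 asks only for "CT diagnosis of ureteral stone with a stone burden less than or equal to 10mm". Nothing requires the stone to be present still at consent or scan, and nothing excludes a patient who has already passed it.

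For secondary objective 2, section 7.3 says "Average time to stone passage for each size category and stone location will be determined", and adds Cox models for factors that affect time to passage. It mentions neither delayed entry, nor a landmark, nor a count of patients who passed a stone before entry.

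Appendix A, whose column alignment is broken in the available text, appears to place consent and scan within one day of the CT. That does not agree with the 10 days in 5.2.

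**The concern.** The clock starts at CT, but a patient can be observed to pass a stone only after entering the study. Someone whose pain has gone and whose stone has passed has less reason to return for a consent discussion and a scan. If such patients stay out, those who enter on day 5, say, are people who had not passed by day 5. Counting them as at risk from day 0 adds person-time in which no event could have been recorded. This is left truncation. It removes short passage times and weakens the contrast between small and large stones.

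It matters for this objective because section 1.1 says no modern passage rates by stone size exist for the period of medical expulsive therapy, and secondary objective 2 is meant to supply them. The smallest stones are the ones most likely to pass in the gap.

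**Working it through.** The plan gives no figure that can be reproduced here. The target of about 100 patients comes without alpha, power or effect size, and the point does not depend on it.

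**Inputs from the documents.** Clock from CT and 42-day horizon (5.2, 5.3, 5.5); scan up to 10 days after CT (5.2); apparent one-day column (Appendix A); 95% passage for stones under 4 mm, taking up to 40 days (1.1).

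**Assumptions.** Exponential passage; entry time uniform over 0 to W days and unrelated to passage time; no competing surgery; all pre-entry passers lost unless stated.

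**Step 1: median and early passage.** With hazard λ, the share of patients who enter is m = (1 − e^(−λW))/(λW). Once everyone has entered, the naive curve is S(t) = e^(−λt)/m. Its median is (ln 2 − ln m)/λ, and 14-day passage is 1 − e^(−14λ)/m.

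For a true median of 7 days, λ = 0.6931/7 = 0.0990 and e^(−14λ) = 0.25.

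- W = 1: m = 0.952, median = 7 + 0.049/0.0990 = 7.5.
- W = 10: m = 0.635, median = 7 + 0.455/0.0990 = 11.6.
- Mixed entry, part over days 0-10 and the rest within a day: m is the weighted mean, for example 0.5 × 0.635 + 0.5 × 0.952 = 0.793. The formula is slightly approximate where the median falls before day 10; simulation gives the same rounded values.

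**Step 2: hazard ratio.** Simulated comparison of true medians of 7 and 21 days (ratio 3.0), using events to day 42 per person-day counted from CT.

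| Entry | m (7-day group) | Naive median (true 7) | Passed by day 14 (true 75%) | Naive hazard ratio (true 3.0) |
|---|---|---|---|---|
| All within 1 day | 0.952 | 7.5 | 73.7% | 2.92 |
| 20% over days 0-10, rest within a day | 0.889 | 8.2 | 71.9% | 2.87 |
| Half over days 0-10, rest within a day | 0.793 | 9.3 | 68.5% | 2.78 |
| All over days 0-10 | 0.635 | 11.6 | 60.6% | 2.57 |

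Counting person-time from entry returns 3.0 in every row.

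**Step 3: the protocol's own passage figure.** Reading 95% as reached by day 40, λ = −ln(0.05)/40 = 0.0749 per day, so 1 − e^(−0.749) = 52.7% of small stones pass by day 10. Mid-size and large stones are assumed to reach 75% and 50% by day 42. All patients enter over days 0-10.

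| Stones | Never enter | Mean days among passers, true to naive | Day-14 passage | Day-42 passage |
|---|---|---|---|---|
| Small | 29.6% | 11.5 to 15.3 (+33%) | 65.0 to 50.2% | 95.7 to 93.9% |
| Mid | 14.8% | 16.3 to 19.5 (+20%) | 37.0 to 26.0% | 75.0 to 70.7% |
| Large | 7.8% | 18.6 to 21.5 (about +15%) | 20.6 to 13.9% | 50.0 to 45.8% |

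**Step 4: sensitivity for small stones.** If only half of the pre-entry passers are lost, the mean goes from 11.5 to 13.0 days (+14%). With entry within one day and all lost, it goes from 11.5 to 11.9 (about +4%). If passage is front-loaded (Weibull shape 0.7), it goes from 8.1 to 13.7 with a 10-day window and from 8.1 to 9.2 with a one-day window.

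**Step 5: does the remedy work?** In the Step 3 setting, left-truncated Kaplan-Meier gives 42-day restricted means of 12.75, 22.71 and 30.36 days, against true values of 12.76, 22.71 and 30.30. The naive values are 16.90, 26.13 and 32.60.

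**The case against.** The strongest reply is that the loss is inferred. Eligibility rests on a CT diagnosis, a patient who has passed the stone is not barred, and imaging that shows its absence is accepted as a passage date. Section 5.1 lets staff approach patients as soon as a stone is suspected, and phone contact is only a possibility for some. The 10 days limit the scan and so are only an upper bound on the delay to consent. If the one-day column in Appendix A governs, the bias is small unless passage is strongly front-loaded. All of this stands, and it makes the size uncertain. It does not remove the point: the plan permits late entry, and with no record of pre-entry passers the sponsor could not show that few were lost.

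A second reply is that about 100 patients over five size bands give noisy estimates anyway. With an assumed 20 per band, a sample median around a true 7 days would range roughly from 3.6 to 12.3. That is fair on practical weight, but this bias runs in one direction and does not shrink as patients are added.

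A reader might also infer that small stones are worst affected on every measure. They are not. With all entering over days 0-10, the median shifts by 4.6 days for a true median of 7 and by 4.9 for a true median of 21 ((0.6931 + 0.1605)/0.0330 = 25.9). At day 42 small stones lose the fewest percentage points, 1.8 against 4.3 and 4.2.

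**Conclusion.** The point holds as a conditional one, confined to the natural-history estimates of secondary objective 2. The plan allows entry after the clock has started and does not allow for it in the analysis. To the extent that pre-entry passers are lost, passage will look too slow, with the largest relative bias in mean time and early passage for small stones. The effect on a 7-day median runs from about half a day (entry within one day) to 4.6 days (everyone entering over days 0-10), and a hazard ratio of 3.0 falls to between 2.9 and 2.6. These figures rest on exponential passage, uniform entry and complete loss; partial loss gives less and front-loaded passage gives more.

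Two stronger readings are not supported. One is that early passers never enter: patients consented at the ED visit are followed almost from the CT, and no rule keeps the others out. The other is that recruitment from both the ED and the Urology office confounds the jet comparison in the primary analysis. The documents give no split by source and no jet or surgery rates by source, both groups are described as presenting with renal colic, and the primary aim is prediction.

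**What to change.** In 7.3, secondary objective 2:

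- State that time to passage is measured from the diagnostic CT (day 0), and that each patient enters the risk set on the date observation starts: the consent date, or the RBUS date if patients without a scan are not followed. Using consent in the latter case would leave losses between consent and scan uncorrected.
- Replace the simple averages by left-truncated Kaplan-Meier estimates for each size category and location, and fit the Cox models with delayed entry. A patient enrolled after passing the stone contributes no time at risk to these analyses and should be listed separately.
- Record on the screening log the eligible patients not enrolled because the stone had already passed.
- Reconcile the 10-day window in 5.2 with the apparent one-day column in Appendix A, since the window largely determines how much the bias can matter.

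The cost is SAP wording, one screening-log item and use of the CT, consent and scan dates. The statistical price is that few patients are at risk in the first days, so early intervals will be wide, above all for the smallest stones. The method also assumes that entry time is unrelated to passage time, which the SAP should say.
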